3.0 Study Endpoints/Events/Outcomes

- 3.1 Primary Endpoint/Event/Outcome: Caregiver self-efficacy and competence
- 3.2 Secondary Endpoint(s)/Event(s)/Outcome(s): Caregiver distress (subjective stress and depressive symptoms), negative health transitions for person with ADRD (falls, wandering), service utilization of person with ADRD (residential care placement, hospitalization).

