Eligibility screening. If caregivers agree to participate, the PI or RC will initiate a brief screening procedure. The following inclusion criteria will be applied for persons with ADRD: 1) English speaking; 2) physician diagnosis or recognition of ADRD (e.g., Alzheimer's disease, Lewy Body disease, fronto-temporal dementia, or stroke/vascular dementia; mild cognitive impairment); 3) not currently receiving care or case management services; and 4) 55 years of age and over.

PROTOCOL TITLE: A Proactive Health Monitoring Intervention for Dementia Caregivers: The eNeighbor

Caregivers of persons with ADRD must: 1) speak English; 2) be 21 years of age and over; 3) self-identify as someone who provides help to the person with ADRD because of their cognitive impairments; 4) self-identify as the person most responsible for providing hands-on care to the person with ADRD or sharing that role with someone else (i.e., the “primary” family caregiver, which can include highly involved kin or non-kin of persons with ADRD; those who share care responsibilities are also eligible); 5) plan to, or ideally wish to, remain in the area for at least 18 months in order to reduce possible loss to follow-up; and 6) indicate a willingness and need to use eNeighbor. To determine eligibility, the E-Neighbor Screening Form will be administered either in-person over the telephone by the PI or RC to determine and identify eligible persons with ADRD and their family caregivers.

Enrollment/Consent and Assent

Within two weeks following the completion of eligibility screening, consent/assent procedures and baseline interviews will be scheduled within 2 weeks for eligible caregivers. Signed informed consent from the eligible family caregiver will take place. Signed informed consent will be offered in-person, via mail, or if deemed most convenient to the family caregiver, via an online consent form.

If a legally authorized representative (LAR) for the person with ADRD is identified other than the family caregiver, we will also obtain signed consent from this individual. For the purposes of efficiency, we will offer an online consent form to review and approve. All online consent and HIPAA forms will be administered via the secure University of Minnesota Google Docs application.

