In instances where ADRD caregivers are terminated from the study, we will determine and document the reason for termination and ask the caregiver to return the eNeighbor system (if applicable). We would not send the caregiver any follow-up surveys/interviews.

14 Risks to Participants**14.1 Foreseeable Risks:**

The consideration of need is potentially stressful, and thus there are possible psychological risks for the caregiver a relative with Alzheimer's disease and related dementia (ADRD). Since the research team has considerable experience providing psychosocial support to dementia caregivers on various research protocols, serious psychological risks are unlikely to occur. The potential social or legal risks for the participants relate only to possible violations of confidentiality. As noted above, HealthSense, Inc. has instituted a robust and secure data privacy system for the remote health monitoring technology.

14.2 Reproduction Risks: Not applicable**14.3 Risks to Others: Not applicable****15 Incomplete Disclosure or Deception****15.1 Incomplete Disclosure or Deception: Not applicable****16 Potential Benefits to Participants****16.1.1 Potential Benefits: There are no direct benefits of participating in the study.****17 Statistical Considerations****17.1 Data Analysis Plan:**

Intensive longitudinal analysis procedures (growth curve modeling) will be utilized to capitalize on the randomized design and the multiple waves of data that will be collected.

17.2 Power Analysis:

The number of ADRD caregivers to be enrolled to address study hypotheses was determined using power analysis procedures that take into account the hierarchical

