21.1.1 Compensation for Research-Related Injury: N/A

21.1.2 Contract Language: N/A

22 Consent Process

22.1 Consent Process (when consent will be obtained):

Within two weeks following the completion of eligibility screening, consent/assent procedures and baseline interviews will be scheduled within 2 weeks for eligible caregivers. Signed informed

PROTOCOL TITLE: A Proactive Health Monitoring Intervention for Dementia Caregivers: The eNeighbor

consent from the eligible family caregiver will take place. Signed informed consent will be offered in-person, via mail, or if deemed most convenient to the family caregiver, via an online consent form. The following IRB approved script will also be administered either in-person or via the telephone in instances where a participating caregiver wishes to complete the consent form via mail or online.

“We are examining the effectiveness of health monitoring technology for family caregivers of persons with memory loss, and we are asking whether you would be interested in helping us with this project. We expect that this technology can help feel family caregivers feel more secure and confident about their relative’s care, will experience reduced stress, and can help their relative stay at home longer.

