“We are asking you to sit down with me to first review and sign the consent form and also to have your relative complete a brief cognitive screening procedure and then complete verbal assent to complete this project. Over the next few days you will be randomly assigned, like the flip of a coin to the group that receives the health monitoring technology system for your relative or the usual care control group. If you are in the group that receives health monitoring technology, we will ask you to work with the Director of Nursing Technology to conduct a visit to the home where your relative with memory loss lives to install the health monitoring technology and learn how to use it. If you are selected to receive health monitoring technology, I will be contacting you monthly to complete some checklists to see how the sensors are working for you and your relative, and then at 6-, 12-, and 18-months to complete a survey and some additional open-ended questions. Everyone will also be asked to help us complete interviews at 6-, 12-, and 18-months. For those assigned to the health monitoring group, we may ask you near the end of the project to sit down with me for around an hour or so to see how well the health monitoring system worked for you or your relative. Also, if you are selected to not receive the health monitoring technology, at the end of this project <mention how long until the end of the project> we will offer the technology to you for free on a first-come, first-serve basis.

“How does this sound? Is this something you might be interested in helping us out with? <if no, then the PI or RC will thank them and end the interview process>”

We will add the following questions to ascertain comprehension of participants:

- “Explain to me what we are asking you to do as part of this project.”
- “What are some of the challenges you think will come up if you decide to participate?”
- “Let’s review how the eNeighbor system works, and then you can ask me questions about it.”
- “Do you have any other questions about your privacy and confidentiality, your rights as a research participant, or any other aspect of participation that I can try and help answer?”

If a legally authorized representative (LAR) for the person with ADRD is identified other than the family caregiver, we will also obtain signed consent from this individual. For the purposes of efficiency, we will offer an online consent form to review and approve. All online consent and

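### The consent script tells prospective caregivers that the team expects gains in confidence and stress, which are self-rated outcomes in an unblinded trial; neutral wording would be a cheap improvement

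*Combined protocol and SAP*

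**What the plan says.** Section 22.1 (Consent Process) gives a script to be spoken to caregivers around the signing of consent. After saying that the team is examining effectiveness, it continues: "We expect that this technology can help feel family caregivers feel more secure and confident" about the relative's care, and adds that caregivers "will experience reduced stress, and can help their relative stay at home longer". It then explains the allocation still to come: "Over the next few days you will be randomly assigned, like the flip of a coin". On who hears it, the delivery sentence reads "script will also be administered either in-person or via the telephone in instances where a participating caregiver wishes to complete the consent form via", and then names the two remote routes, post and internet.

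Other sections bear on this wording:

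- Section 3.1: "Primary Endpoint/Event/Outcome: Caregiver self-efficacy and competence". Section 3.2 lists subjective stress, depressive symptoms, falls, wandering, residential placement and hospitalization as secondary.
- Section 5.2 (Treatment/Intervention Period): randomization follows the baseline interview, and the caregiver is told the assigned arm within days.
- Section 5.3: the caregiver is the respondent for every survey. The principal investigator or coordinators, who also disclose allocation, complete the follow-up. No masking is described.
- Section 5.2 (Eligibility screening): caregivers must "indicate a willingness and need to use eNeighbor". Section 9.1 asks for willingness only.
- Section 16.1.1: "There are no direct benefits of participating in the study".
- Section 5.3 (Final Study Visit/Survey): the offer of the system to controls is withdrawn if it proves to increase caregivers' emotional stress or depressive symptoms.

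**The concern.** A trial that rests on self-rated confidence and stress, with allocation known to the rater, is open to expectancy in the answers. Here the script supplies the expectation, and in terms close to the constructs later measured. A caregiver given the system may report the gain that was forecast. A control who wanted the system may report against having missed it. Neither response reflects an effect of the technology, and both would fall into the treatment contrast for the primary endpoint. Section 17 plans no measure of expectancy, so the analysis could not separate it from benefit.

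There is also a matter of consistency. The script describes likely benefits, section 16.1.1 says participation has none, and section 5.3 provides for possible harm. Section 2.3 describes the effectiveness of such technological aids for these caregivers as largely unknown, and the script's sentence does not convey that uncertainty.

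**Working it through.** The point is textual. The check sets the script beside the endpoints and then follows how a bias could reach the contrast.

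**1. Script against endpoints**

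| Expectation in the script (22.1) | Endpoint echoed (3.1, 3.2) | Status |
|---|---|---|
| More secure and confident about the relative's care | Caregiver self-efficacy and competence | Primary |
| Reduced stress | Subjective stress | Secondary |
| Relative stays at home longer | Residential placement | Secondary |
| (not mentioned) | Depressive symptoms, falls, wandering, hospitalization | Secondary |

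The script therefore echoes the primary endpoint and parts of the secondary set. It does not recite Hypotheses 1 to 3 in full.

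**2. Order of events**

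Script and consent, then baseline survey, then randomization, then disclosure of the arm, then self-report at 6, 12 and 18 months. Both arms receive the same script at the same stage.

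**3. Where bias can enter**

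Let the script and all other expectancy shift reported scores by d_T in the treated arm and d_C in controls. The observed contrast is

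(true mean T + d_T) − (true mean C + d_C) = true effect + (d_T − d_C).

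If the script moves both arms equally, d_T − d_C = 0 and the contrast is unaffected. Only a differential response after allocation is known matters. Write that difference as

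d_T − d_C = b_open + b_script,

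where b_open is the expectancy that comes from open allocation, home installation and monthly contact, and b_script is what this sentence adds. Rewording acts on b_script alone.

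**4. Can b_script be sized?**

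No. The documents give neither b_open nor b_script, nor any measure of expectancy from which to infer them.

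**5. Script against sections 16.1.1 and 5.3**

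Section 16.1.1 concerns the benefit of participating, which includes being a control. The script concerns the technology and is framed as an expectation. The two do not assert opposite facts, but a caregiver would take different messages from them. Section 5.3 recognises that stress or depressive symptoms could increase, and the script's sentence forecasts the reverse for stress.

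**6. Who hears it**

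The sentence on delivery can be parsed in two ways: in person for in-person consent and by telephone for mail or online consent, which covers everyone; or only for caregivers consenting by mail or online. The first is more natural, since the script asks the caregiver to sit down with the speaker and no other caregiver consent script is given. The text does not settle it.

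**The case against.** The strongest reply is that the sentence is a small part of a larger and unavoidable problem. Caregivers are chosen for wanting the system, know whether they have it, and are visited and telephoned about it. Neutral wording leaves all of that in place. This stands, and it limits what the change can achieve.

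Four stronger readings are tempting, and the documents do not support them.

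- *A quantified false-positive rate.* Taking 200 less 20% attrition (section 17.2), 200 × 0.80 / 2 = 80 per arm. With no true effect and a two-sided 5% t test, assumed differential shifts of 0.1, 0.2 and 0.3 SD give rejection rates of 9.6%, 24% and 47%. The arithmetic is right, but the shifts are assumptions about unblinded self-report as a whole (b_open + b_script), not about this sentence. Had the sentence alone added 0.02 or 0.05 SD, the same test would give 5.2% or 6.1%. None of these figures measures the defect.
- *Bias certainly favours eNeighbor.* That is the likely direction. But expectations raised and not met could lower treated caregivers' ratings, and the promise of a free system at the end could soften controls' disappointment.
- *A flat contradiction of section 16.1.1.* The script is hedged and follows a statement that effectiveness is under study. This is an inconsistency of message.
- *Every caregiver is exposed, and each was selected for need.* The first depends on the parsing above. The second rests on section 5.2 alone, because section 9.1 requires only willingness.

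The consent form itself is not available for this review. Section 5.3 says it carries a clarification about a possible negative effect, so caregivers may read more balanced text than they hear. That softens the point; it does not justify the spoken sentence.

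**Conclusion.** The point holds as a cheap improvement. Before randomization the script forecasts gains that match the self-rated primary endpoint and parts of the secondary endpoints, to people who will later know their arm and rate themselves. This is an avoidable addition to expectancy. Its direction probably favours eNeighbor, its size cannot be derived from the documents, and removing it will not make the self-rated comparison free of expectancy. Outcomes such as nursing home admission and hospitalization are less open to it than the rating scales, although caregivers report those too.

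The conclusion assumes that the script is used as printed and that no masking of caregivers or outcome collectors exists beyond what the protocol describes.

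**What to change.** Replace the expectation sentence in section 22.1 with neutral wording, for example:

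> *We do not know whether this technology helps, makes no difference, or adds stress for family caregivers or their relatives; that is why we are comparing it with usual care.*

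Align that wording with section 16.1.1, and state in section 22.1 which consent routes (in person, mail, online) use the script.

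If caregivers have already consented under the present wording, the amendment cannot undo their exposure and leaves two groups who heard different scripts. Record the date of change and report the wording as a limitation on the self-rated outcomes.

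The cost is one script amendment to the ethics board and an invitation that may persuade slightly fewer people. Sample size, visits and the planned models are unchanged.
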